13.1 Data Collection and Management Responsibilities

Data will be collected on paper CRFs and an Excel database will be created and used to electronically store data. The Excel database will consist of separate Excel files for each study assessment, all of which will be stored in NYULH's secure research drive, individually password protected, and accessible only to study team members with access granted to the folder (path: R:\[name]\FUS\Database). These study team members may include, but are not limited to, the Principal Investigator, research coordinator(s), research assistant(s), study physicians, statisticians, and postdoctoral researchers. Only study IDs will be used throughout the database. Subject names, birthdays, and other personally identifying information will not be retained electronically. The creation of this database will aid in preliminary and future safety and other data analyses.

Of note, only data from subjects who completed all study procedures will be retained in this Excel database. Information from screen failures and subjects who terminated early will not be maintained electronically.

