Statistical Analysis	Because this is a pilot feasibility study, we will examine results after the first 12 participants with good quality imaging data who have completed both phases, and will either continue the study unchanged or, if no signal is detected by fMRI or symptom change, we will switch to administering 3 sessions of PLIFUS or sham over 5 days. We will define our threshold for signal detection as an effect size of 0.5 or greater for the comparison between treatment groups (PLIFUS or sham) of change of biomarkers (fMRI and symptom severity) from baseline to post-treatment. All results will be considered exploratory. Formal statistical analyses will be performed using standard methods for a random-over crossover design; safety outcomes will be descriptive.

Schematic of Study Design

1 Key Roles

[name]

Department of Psychiatry, NYU Langone Medical Center
[name]
[name]
[contact]
[contact]

[name] (Co-PI)

Department of Psychiatry, NYU Langone Medical Center
[name]
[name]
[contact]
[contact]

[name]

Department of Psychiatry, NYU Langone Medical Center
[name]
[name]
[contact]
[contact]

[name], Statistician

Department of Population Health, NYU Langone Health
[name]
[name]
[contact]
[contact]

F. [name]

Department of Child and Adolescent Psychiatry, NYU Langone Medical Center
[name]
[name]
[contact]
[contact]

2 Introduction, Background Information and Scientific Rationale

2.1 *Background Information and Relevant Literature*

2.1.1 **The Need for New Treatment Approaches in Schizophrenia**

Schizophrenia is a disabling chronic illness characterized by psychosis (delusions and hallucinations), negative symptoms (apathy and reduced emotional expression) and cognitive deficits. Antipsychotic medications, which block dopamine transmission, substantially improves delusions and hallucinations in approximately 60% of patients, but side effects are poorly tolerated and relapse is common ¹. Psychosis can be very distressing for patients and their families, often results in hospitalization, and may contribute to violence. Currently there is no effective treatment for negative symptoms and cognitive deficits.

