6.1.8 Dose Adjustments/Modifications/Delays

If change in GPi functional connectivity or change in symptoms is not greater following PLIFUS compared to sham with an effect size of at least 0.5 in the first 12 completers, the number of sessions (PLIFUS and sham) will be increased from 1 to 3 for 4 additional participants.

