7.9 Assessment of Safety

7.10 Specification of Safety Parameters

Safety will be assessed by close monitoring by a study psychiatrist during and for 1 hour after each sonication/sham session by assessment of psychiatric symptoms and side effects (SAFTEE & addendum). SAFTEE, SAFTEE addendum, and CSSRS will be repeated one day and one week after each session. The difference between post-sonication and post-sham safety measures will be assessed for safety. In addition to serious adverse events that will be reported immediately, these data will be provided to the DSMB after the first 8 completers. If the dose is increased to 3 sessions, safety data will be provided to the DSMB after the 4 completers at the higher dose.

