A study psychiatrist will be present during all sessions of PLIFUS and sham. Participants will be monitored during and after sonication until psychiatrically cleared by the study psychiatrist 1 hour after completion of each session. Participants will be contacted 24-48 hours and 7 days after each treatment period and symptoms, side effects and suicidality assessed.

9 Statistical Considerations

This is a pilot study intended to obtain preliminary data to guide future studies. The analysis will primarily be descriptive for this purpose and, due to the small sample size, effect sizes will be the primary signal of target engagement. Consistent with other studies in the field, we have selected an effect size of 0.5 as our threshold. In addition, there is a pre-planned review of results after completion of the first 5 participants; the administration of PLIFUS/sham will be increased from one session to three sessions over 5 days if an effect size of 0.5 or greater with PLIFUS is not detected in change from baseline in GPi functional connectivity or symptom response compared to sham.

The primary statistical analysis will be performed in completers without imputation of missing data and will be change in primary outcomes (GPi functional connectivity and symptom severity) from baseline to the first measure post-sonication or sham (immediately post-sonication for symptoms; 10-30 minutes for fMRI). PLIFUS and sham PLIFUS will be compared using a linear mixed effects model with baseline measures (GPI functional connectivity and severity of psychotic symptoms) as continuous variables; treatment (PLIFUS or sham) and sequence as categorical variables; and participant as a random effect. Similar secondary exploratory analyses will be performed at additional time points (symptom severity during sonication, 60 minutes, 1 day and 7 days after sonication). Secondary analyses of other outcome measures (BPRS total score, PSYRATS and CGI) will be analyzed following the same approach. Safety measures, including the SAFTEE and C-SSRS will be summarized descriptively. If the study design is adapted (sonication increased to 3 sessions) after the first 12 completers with good quality imaging data, results from the first 12 completers and subsequent 4 participants will be analyzed separately.

Sample Size

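### The database meant to support safety analyses keeps completers only, and no section says who belongs in the safety summary

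*Combined protocol and SAP*

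**What the plan says.** Section 13.1 has data recorded on paper case report forms and then stored in Excel, one file per assessment. It gives the purpose: "The creation of this database will aid in preliminary and future safety and other data analyses". The next paragraph restricts the content: "only data from subjects who completed all study procedures will be retained in this Excel database", and adds: "Information from screen failures and subjects who terminated early will not be maintained electronically". It makes no exception for people who had already received PLIFUS or sham.

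The safety analysis is described in three places:

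- Section 9: "Safety measures, including the SAFTEE and C-SSRS will be summarized descriptively".
- Protocol Summary, Statistical Analysis: "safety outcomes will be descriptive".
- Section 7.10: "The difference between post-sonication and post-sham safety measures will be assessed for safety".

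None of the three names a population. Section 9 confines the primary statistical analysis to completers, and section 6.1.9 defines an evaluable participant as one who finished all sessions. Neither rule is applied to safety.

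**The concern.** Tolerability and safety are part of the primary objective (section 3.1), and feasibility and tolerability are the overall purpose (section 3). Section 2.2.2 says PLIFUS has not, to the investigators' knowledge, been studied in schizophrenia, and section 2.4.1 accepts that symptoms might worsen.

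Leaving the trial can depend on the outcome being summarised. Section 5.8.1 lets an adverse event end participation, and section 2.4.1 stops a sonication when symptoms worsen beyond a set amount or distress appears. Enrolment continues until there are 12 completers with good imaging (Protocol Summary, Population), so those who leave are replaced.

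If the final tolerability table, the comparison of conditions or the archived dataset (section 12.4) comes from the Excel files, the people most informative about intolerance are missing. The number who started but did not finish also cannot be seen.

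**Working it through.** The plan states no figure to reproduce. The 12 completers rest on feasibility and cost (section 9, Sample Size), and no dropout rate is given. The check is a comparison of the text, followed by illustrations on stated assumptions.

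**Text, side by side**

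1. Safety data on treated leavers are sought: assessments at 24-48 hours and 7 days after at least one session (5.8.2), and SAFTEE, C-SSRS, AHRS, DESA and BPRS at early termination (7.2.6).
2. They are recorded and kept on paper: adverse events go on the case report form (7.12), which is the primary instrument (10), and study documents are retained (13.2).
3. They are excluded from the one dataset described as serving safety analyses (13.1).
4. Other electronic systems are hinted at (a data collection system in 7.12, a DCC in 7.13, study databases in 12.4), but no section says that any of them holds leavers' ratings.
5. The rule is stricter than the evaluable definition in 6.1.9. Read literally, someone who had both sessions but missed a follow-up procedure is also dropped.

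**How many people**

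To reach 12 completers with early termination rate d, enrolment is 12/(1 − d), rounded up. Assumed d of 10%, 20% and 30% gives 14, 15 and 18, so up to 2, 3 or 6 people fall outside the database (fewer if some leave before any session).

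**Effect on the summary**

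Let n be the number of completers and k the number of treated leavers. Assume no completer has an event and, as the worst case, every leaver does. The database shows 0/n and 100% completion. All treated show an event rate of k/(n + k) and completion of n/(n + k). The case n = 15 allows for completers with poor imaging, who stay in the database while enrolment continues.

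| k | Events, n = 12 | Completion, n = 12 | Events, n = 15 | Completion, n = 15 |
|---|---|---|---|---|
| 1 | 1/13 = 7.7% | 92.3% | 1/16 = 6.3% | 93.8% |
| 2 | 2/14 = 14.3% | 85.7% | 2/17 = 11.8% | 88.2% |
| 3 | 3/15 = 20.0% | 80.0% | 3/18 = 16.7% | 83.3% |
| 4 | 4/16 = 25.0% | 75.0% | 4/19 = 21.1% | 78.9% |

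Exact (Clopper-Pearson) 95% intervals: 0/12, 0 to 26.5%; 1/13, 0.2% to 36.0%; 2/14, 1.8% to 42.8%; 4/16, 7.3% to 52.4%; 0/15, 0 to 21.8%; 4/19, 6.1% to 45.6%. They overlap throughout.

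**Milder assumptions, n = 12.** If half the leavers had an event: 1/14 = 7.1% with two leavers and 2/16 = 12.5% with four. If none did, the event rate is 0 either way, but completion still reads 100% instead of 92.3% to 75.0%.

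**By condition.** Suppose two people leave with an event after a first session that was PLIFUS. Fourteen people received PLIFUS and 12 received sham: 2/14 (14.3%) against 0/12. The database gives 0/12 against 0/12.

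**Three-session phase.** Section 7.10 counts completers ("safety data will be provided to the DSMB after the 4 completers at the higher dose"), whereas section 6.1.8 counts participants ("will be increased from 1 to 3 for 4 additional participants"). One leaver with an event changes 0/4 to 1/5 (20%) on the first reading and 0/3 to 1/4 (25%) on the second.

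**The case against.** The strongest reply is that section 13.1 says the database will help with safety analyses, not that it is their only source. Everything needed for a full table exists elsewhere: adverse events are on paper, all of them are tabulated for the IRB and DSMB, and retention is reported to the DSMB (7.15). Oversight during the trial is not affected. This stands, and it is why the point is a risk only. It does not settle who is in the final summary, because 7.15 governs oversight reports and names no analysis population.

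The illustrations are also constructed. The documents' only background rate is mild, transient side effects in 3.3% of 704 subjects, with no serious events (2.2.2). Applied to 14 people, that is 0.033 × 14 ≈ 0.5 people with any side effect, not necessarily one who leaves. This is a fair caution against the upper rows of the table, although those subjects did not have schizophrenia.

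Three smaller points also stand:

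- Stopping a sonication (2.4.1) is not the same as ending participation.
- If the comparison in 7.10 is made within person, someone with one session cannot contribute whatever the database holds. Event counts by condition would still include that person.
- A privacy reason for the exclusion could sit in the consent form, which was not available. The protocol itself gives none: 13.1 uses study IDs only, and 12.4 allows use of data collected before authorization is revoked.

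**Conclusion.** The concern holds. Section 13.1 sets an explicit completers-only rule for the dataset it offers for safety analyses, and no section defines a safety population that would override it. A summary taken from that dataset would leave out treated people whose departure may itself be a safety outcome, and it would show full completion by construction.

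The size cannot be known from the documents. In the assumed worst case of one to four treated leavers, an apparent 0% becomes 7.7% to 25.0% with 12 completers, or 6.3% to 21.1% with 15. If no leaver had an event, only the completion figure is distorted. The conclusion depends on the summary being drawn from the Excel files, which the documents neither require nor rule out. It should be fixed, because a primary objective ought not to depend on an unwritten decision to go back to paper.

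**What to change.** - **Section 13.1:** keep de-identified electronic data for every participant who received any PLIFUS or sham session, whether or not they completed.
- **Section 9:** define the safety set as all such participants, summarised by condition received. The completer set can stay for the target-engagement analysis.
- **Reporting:** give the numbers enrolled, treated, completed and withdrawn, with reasons for withdrawal.
- **Three-session phase:** reconcile the completer wording in 7.10 with the participant wording in 6.1.8, so that the denominator is clear.

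The cost is a few more data rows and a short amendment. No visits or identifiers are added, since 13.1 already uses study IDs only. The one drawback for the sponsor is that tolerability and completion figures may look less favourable.

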3.1 Primary Objective

To evaluate tolerability, safety and evidence of target engagement (functional connectivity and symptom change) of a single session of PLIFUS targeting the right Gpi in individuals with schizophrenia compared to sham.

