5.8.2 Handling of Participant Withdrawals or Termination

If participants withdraw or are terminated before completion of the study, we will attempt to conduct the safety assessments at 24-48 hours and 7 days if the participant experienced one session.

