6.1.9 Duration of Therapy

2 sessions of PLIFUS/sham administration (delivered over a total of 10 minutes). An evaluable participant will be defined as having completed all sonication/sham sessions.

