7.2.6 Withdrawal/Early Termination Visit*

If a participant withdraws or terminates early, the following assessments will be completed:

- AHRS and DESA
- SAFTEE & addendum

- C-SSRS
- BPRS

*All remote visits will take place over WebEx, a secure video conferencing platform.

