12.4 Participant and Data Confidentiality

Information about study subjects will be kept confidential and managed according to the requirements of the Health Insurance Portability and Accountability Act of 1996 (HIPAA). Those regulations require a signed subject authorization informing the subject of the following:

- What protected health information (PHI) will be collected from subjects in this study
- Who will have access to that information and why
- Who will use or disclose that information
- The rights of a research subject to revoke their authorization for use of their PHI.

In the event that a subject revokes authorization to collect or use PHI, the investigator, by regulation, retains the ability to use all information collected prior to the revocation of subject authorization. For subjects that have revoked authorization to collect or use PHI, attempts should be made to obtain permission to collect at least vital status (i.e. that the subject is alive) at the end of their scheduled study period.

Participant confidentiality is strictly held in trust by the participating investigators and their staff. This confidentiality covers clinical information relating to participants. Therefore, the study protocol, documentation, data, and all other information generated will be held in strict confidence. No information concerning the study or the data will be released to any unauthorized third party.

The IRB may inspect all documents and records required to be maintained by the investigator, including but not limited to, medical records (office, clinic, or hospital).

The study participant's contact information will be securely stored for internal use during the study. At the end of the study, all records will continue to be kept in a secure location for as long a period as dictated by local IRB and Institutional regulations.

Study participant research data, which is for purposes of statistical analysis and scientific reporting, will be stored at NYU Langone Medical Center. This will not include the participant's contact or identifying information. Rather, individual participants and their research data will be identified by a unique study identification number. Data used for statistical analysis, including imaging analysis, will be de-identified. The study data entry will be secured and password protected. At the end of the study, all study databases will be de-identified and archived at the NYU Langone Medical Center.

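### The electronic database leaves out treated participants who stop early, so safety summaries drawn from it would omit them

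*Combined protocol and SAP*

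**What the plan says.** Section 13.1 has data recorded on paper forms and then stored in Excel, with one file per assessment. It gives the purpose: "The creation of this database will aid in preliminary and future safety and other data analyses". It then restricts who is kept: "only data from subjects who completed all study procedures will be retained in this Excel database". The next sentence adds: "Information from screen failures and subjects who terminated early will not be maintained electronically".

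Other sections treat people who leave as a source of safety information:

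- Section 7.2.6: "If a participant withdraws or terminates early, the following assessments will be completed". The list that follows is AHRS, DESA, SAFTEE with its addendum, C-SSRS and BPRS.
- Section 5.8.2: "we will attempt to conduct the safety assessments at 24-48 hours and 7 days if the participant experienced one session".
- Section 3.1 opens the primary objective with "To evaluate tolerability, safety and evidence of target engagement".
- Section 7.10 plans to compare safety measures after sonication with those after sham, and Section 9 plans a descriptive safety summary. Neither is limited to completers, and neither names a safety population. Section 9 limits only the primary analysis to completers.

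The Protocol Summary (Population) and Section 5.7 have enrolment continue until 12 participants have completed; the Summary adds that their imaging must be of good quality.

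**The concern.** The rule in 13.1 is about data storage, but it also decides who can appear in any safety table built from the database. Section 9 names no safety set, so 13.1 supplies one by default, and that set consists of completers.

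Leaving early is itself a tolerability outcome, and people who react badly may be more likely to leave. Section 2.4.1 says that PLIFUS has not been studied before in schizophrenia and that symptoms might worsen. Because enrolment continues until there are 12 completers, the retained file would look complete at 12 whatever the number who left. Neither the count of leavers nor their scores would be visible in it.

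**Working it through.** **Step 1: compare the sections.** Sections 5.8.2 and 7.2.6 obtain SAFTEE, C-SSRS, AHRS and DESA data from a participant who had one session and left. Sections 7.10 and 9 would use such data, since they set no completer limit. Section 13.1 keeps the same data out of the file meant to help with safety analyses. It describes no other electronic store for the assessment scores.

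**Step 2: look for a figure to reproduce.** There is none. The 12 completers are justified in Section 9 by feasibility and budget, and the plan states no dropout rate and no rate of worsening. What follows is an illustration with assumed counts.

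**Step 3: formula.** Let n be completers, c their events, m treated leavers and e the leavers' events.

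- Database rate: c/n.
- All-treated rate: (c + e)/(n + m).
- Difference (all treated minus database): m/(n + m) × (e/m − c/n).

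The difference is zero if leavers and completers have the same event rate. The database understates risk when leavers do worse and overstates it when they do better.

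**Step 4: numbers.** n = 12 comes from the Protocol Summary and Sections 5.7 and 9; c = 0, m and e are assumed. Intervals are exact (Clopper-Pearson) 95%. For 0/12 the upper limit is 1 − 0.025^(1/12) = 0.265. For 1/13 the lower limit is 1 − 0.975^(1/13) = 0.002, and the upper limit is the 97.5th percentile of Beta(2, 12), 0.360.

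| Leavers m | Events e | Database | All treated |
|---|---|---|---|
| 1 | 1 | 0/12 = 0% (0 to 26.5%) | 1/13 = 7.7% (0.2 to 36.0%) |
| 2 | 2 | 0/12 | 2/14 = 14.3% (1.8 to 42.8%) |
| 3 | 1 | 0/12 | 1/15 = 6.7% (0.2 to 31.9%) |
| 3 | 3 | 0/12 | 3/15 = 20.0% (4.3 to 48.1%) |
| 4 | 4 | 0/12 | 4/16 = 25.0% (7.3 to 52.4%) |

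The first row is the main illustration. Rows where every leaver has an event and no completer does are the extreme case. In the opposite direction, one event among completers and one event-free leaver would give 1/12 = 8.3% in the database against 1/13 = 7.7%.

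**Step 5: by condition.** Suppose the single leaver in the first row had only the PLIFUS session. By condition started, the result is 1/13 for PLIFUS and 0/12 for sham. The database would show 0/12 for both, so the contrast planned in 7.10 would lose its only event.

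**The case against.** The strongest reply is that the safety information exists outside Excel. All adverse events go on case report forms (7.12), which are the primary collection instrument (10), and study documents are retained (13.2). The DSMB receives unblinded safety reports that include AHRS and DESA changes, reviews retention, and, with the IRB, gets tabulated adverse events (7.15). Section 13.1 says only that the database will aid analyses; nothing makes it the sole source for the summaries in 7.10 and 9. The trial is a small descriptive pilot, every count above is assumed, and the intervals overlap heavily.

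All of that stands, and it limits the size of the point. It does not remove it: those routes serve oversight and archiving, and they do not make the electronic file complete.

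Some stronger readings are tempting but not supported:

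- *Safety events would be lost or hidden from oversight.* The sections just cited show otherwise.
- *13.1 contradicts the definition of evaluable.* Section 6.1.9 says "An evaluable participant will be defined as having completed all sonication/sham sessions", and a strict reading of 13.1 would drop someone who had both sessions but missed a follow-up. The next sentence of 13.1, however, names those left out as screen failures and early terminators, and such a person is neither. The wording is ambiguous, not contradictory.
- *13.1 conflicts with the confidentiality section.* Section 12.4 says that after revocation the investigator "retains the ability to use all information collected prior to the revocation of subject authorization". That permits use and says nothing about storage format, so there is no conflict.
- *The primary analysis is compromised by 13.1.* Its restriction to completers is a separate, explicit choice in Section 9.
- *AHRS and DESA are neglected as safety measures.* Section 4.2.2 leaves them off its safety list, but they are collected at every relevant visit and sent to the DSMB. This is a labelling inconsistency.

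**Conclusion.** The point holds. As written, 13.1 excludes treated early terminators from the electronic data intended to support safety analyses, although the plan goes out of its way to assess them and counts safety and tolerability in its primary objective. This is a stated rule, not a missing detail.

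The consequence is minor to moderate. It depends on two assumptions: that safety summaries would in fact be drawn from the database, and that leavers differ from completers in their event rate. The documents establish neither. If both hold, a single leaver can turn a 7.7% observed rate into zero. At this sample size the intervals are wide either way, so what is lost is mainly an accurate count and denominator.

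**What to change.** Amend Section 13.1 along these lines: *All data from every randomized participant, including early terminators and those with missed procedures, will be retained electronically under study ID; only screen-failure data will be excluded.* Randomized is a better boundary than treated, because the Schedule of Events places randomization at the MRI visit, before the first session, and 7.12 records events from consent onward. This wording also removes the ambiguity about missed follow-up visits.

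In Section 9, state that:

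- safety summaries use all participants who started at least one PLIFUS or sham session;
- the denominator for each condition is the number who started that condition;
- the number of early terminations and their reasons will be reported.

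Leave the completer primary analysis as it is. As an optional small edit, add AHRS and DESA to the safety measures in 4.2.2, in line with their use in 2.4.1 and 7.15.

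The cost is a few sentences of amendment and entry of existing paper data for a few participants. No new assessments are needed.
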